#### 8.3.3.2 Suspected Adverse Drug Reactions/Adverse Reactions

All noxious and unintended responses to a medicinal product or study treatment related to any dose should be considered suspected ADRs. The phrase "responses to a medicinal product" means that a causal relationship between a medicinal product or study treatment and an AE is at least a reasonable possibility. A suspected ADR with a causal relationship of "definitely" will be labeled as an AR; thus, ARs are a subset of suspected ADRs.

#### 8.3.4 Assessment of Causality of Adverse Event

The investigator is required to provide a causality assessment for each AE reported to the sponsor. The sponsor will consider the investigator's causality assessment and also provide its own assessment.

Causal relationship to the study drug will be established according to medical judgment on whether there is a reasonable possibility of a causal relationship between the AE and study treatment administration:

The investigator must determine and classify the AE causality according to the following categories:

Unrelated/Not related: there is not a reasonable possibility of causal relationship between the AE and the study treatment.

**Possibly related:** there is evidence to suggest a causal relationship between the study treatment and the AE.

**Definitively related:** there is a reason to conclude that the study treatment caused the AE.

Criteria to assess the causal relationship should take into account of the following conditions:

- 1. a plausible temporal sequence from the study treatment administration to the AE onset;
- 6. whether the event follows a known response pattern to the suspected treatment;
- 7. whether the AE could be reasonably explained by the subject's clinical state. comorbidities, or concomitant medications, as well as
- 8. the occurrence of improvement on stopping/reducing the treatment (positive dechallenge) and/or reappearance of the event on repeated exposure (positive rechallenge).

For expedited safety reporting purposes, AEs assessed as either "definitively related" or "possibly related" will be considered just RELATED or POTENTIALLY RELATED.

#### 8.3.5 Severity of Adverse Event or Suspected Adverse Drug Reaction

Adverse events and suspected ADRs will be classified depending on their severity according to the following definitions:

Mild: the subject is aware of signs or symptoms causing minimum discomfort but no disruption of usual daily activities consistent with what would be expected in an uneventful postoperative course

**Moderate**: the AE is sufficiently discomforting to the subject that it interferes with usual daily activities consistent with what would be expected in an uneventful postoperative course (disturbing)

**Severe**: due to the AE, the subject is unable to perform usual daily activities consistent with what would be expected in an uneventful postoperative course (prevents)

AE and suspected ADR severity gradation must be distinguished from AE and suspected ADR seriousness gradation, which is defined according to event consequence. For example, headache can be mild, moderate, or severe but not necessarily serious in all these cases.

The investigator will be responsible for assessing the AE and suspected ADR intensity during the clinical trial, taking into account current criteria included in this section and according to the investigator's medical judgment.

#### 8.3.6 Expectedness of Adverse Event or Suspected Adverse Drug Reaction

An AE or suspected ADR is considered "unexpected" if the nature, seriousness, severity, or outcome of the reaction(s) is not consistent with the reference safety information (e.g., IB or PI). The expectedness shall be determined by the sponsor according to the reference document (1,2) for any serious suspected ADRs (potentially related SAEs) for expedited safety reporting purposes.

#### 8.3.7 Seriousness of Adverse Event or Suspected Adverse Drug Reaction

An AE or suspected ADR is considered "serious" if, in the view of either the investigator or sponsor, it results in any of the following outcomes:

- Death
- Life-threatening AE (life-threatening in the definition of "serious" refers to an event in which the subject was at risk of death at the time of the event; it does not refer to an event which hypothetically might have caused death if it were more severe)
- In-patient hospitalization or prolongation of existing hospitalization\*
- A persistent or significant incapacity or substantial disruption of the ability to conduct normal life functions
- A congenital anomaly/birth defect
- An important medical event (important medical event in the definition of "serious" refers to those events which may not be immediately life-threatening, or result in death, or hospitalization, but from medical and scientific judgment may jeopardize the subject or/and may require medical or surgical intervention to prevent one of the other outcomes listed above).

The following hospitalizations should not be reported as SAEs:

- hospitalization or prolongation of hospitalization needed for procedures required by the clinical trial protocol.
- hospitalization or prolongation of hospitalization as part of a routine procedure followed by the center.
- hospitalization for a survey visit, annual physicals, or social reasons.
- Elective or pre-planned hospitalizations for a pre-existing condition that had not worsened from baseline (e.g., elective or scheduled surgery arranged prior to start of the study).

\*Hospitalization is to be considered only for a hospital stay of equal to or more than 24 hours.

admissions not associated with an AE (e.g., social hospitalization for purposes of respite care).

This definition permits either the sponsor or the investigator to decide whether an event is "serious". If either the sponsor or the investigator believes that the event is serious, the event must be considered "serious" and evaluated by the sponsor for expedited reporting.

#### 8.3.8 Adverse Event Documentation

All AEs and SAEs occurring after the subject has signed the ICF through the final study visit (i.e., Post-operative Day 30±7 days) must be fully recorded in the subject's eCRF, and paper SAE report form (if serious) as well as in the medical record. If no AE has occurred during the study period, this should also be indicated in the eCRF.

It is the responsibility of the investigator to ensure that AEs are appropriately recorded.

At each visit, AEs will be elicited by asking the individual a non-leading question such as "Do you feel different in any way since the last visit?" Moreover, AEs will also be collected through directly observed events or spontaneously volunteered by the subject. Clearly related signs, symptoms, and abnormal diagnostic procedures should preferably be grouped together and recorded as a single diagnosis or syndrome wherever possible.

The following variables must be recorded in the AE eCRF:

- The verbatim term (a diagnosis is preferred)
- Date/time of onset
- Date/time of resolution
- Severity (mild, moderate, severe)
- Causality (unrelated, possibly related, definitely related)\*
- Seriousness (yes, no)
- Action taken (with regard to study treatment)
- Other action (to treat the event)
- Outcome and sequel (follow-up on AE)

In addition to the investigator's own description of the AEs (verbatim term), each AE will be encoded according to the Medical Dictionary for Regulatory Activities (MedDRA®).

\*Causality assessment will be made only when the AE occurs after the subject has received the study treatment. An AE occurring before subject's exposure to study treatment will be always labeled as "unrelated".

For example, a laboratory test abnormality considered clinically relevant (e.g., causing the subject to withdraw from the study, requiring treatment or causing apparent clinical manifestations) or judged clinically relevant in the context of the subject's medical condition by the investigator, should be reported as an AE. Each event must be described in detail along with start and stop dates, severity, relationship to IP, action taken and outcome. Each event must be adequately supported by documentation as it appears in the subject's medical or case file

#### 8.3.9 Reporting of Serious Adverse Events

#### 8.3.9.1 Reporting of Serious Adverse Events

[figure not shown]
Any SAE (see Section 8.3.7) that occurs after signing the study ICF through the final study visit (i.e., Post-operative Day 30± 7 days) must be expeditiously reported whether or not considered attributable to the study treatment. Each SAE must be fully recorded in the subject's eCRF and additionally reported in a timely manner using the paper SAE Report Form.

SAEs will be reported using the designated paper SAE Report Form. When the investigator becomes aware of an SAE, she/he must submit a completed, signed and dated paper SAE Report Form (in English) within 24 hours to the sponsor by email/fax.

The date of this SAE discovery by the site staff should be documented in the source documents (i.e., medical records).

Each SAE must be followed up until resolution or stabilization. After the initial report, all relevant information for SAE follow-up, and for the outcome, must also be supplied to the sponsor in a timely manner (within 3 days from its identification or within 24 hours for relevant new information) by means of the paper SAE Report Form. In addition, the sponsor or contract research organization may request additional information and/or reports.

All paper SAE Report Forms must be reported to Grifols via email to:

When required, and according to local law and regulations, SAEs must be reported to the IRB/EC and regulatory authorities.

#### 8.3.9.2 Reporting Pregnancy

Pregnancies occurring during the course of the study will not be considered an AE unless a relation to the study drug is suspected. In any case, a Pregnancy Report Form must be completed and sent as soon as possible to the sponsor for any pregnancies that occur in a female subject or partner of a male subject from time of consent through the final study visit (i.e., end of study). A copy of the form should be filed at the study site for follow-up until the end of the pregnancy. Any pregnancy must be followed by the investigator until delivery or to the end of pregnancy. Any anomalies, complications, abnormal outcomes, or birth defect observed in the child must be reported as an SAE (see email address or fax number in Section 8.3.9.1) within 24 hours of the investigator or study personnel's first knowledge.

# 8.4 Type and Duration of the Follow-Up of Subjects after Adverse Events

In so far as is possible, all individuals will be followed up until the AE or suspected ADR has been resolved. If an AE/suspected ADR/SAE is present when the subject has completed the study, the course of the event must be followed until the final outcome is known, or the event has been stabilized and no further change is expected and the investigator decides that no further follow-up is necessary.

Any SAE that occurs after the end of the clinical study or after study completion due to early termination will not be actively collected. However, if such cases are reported by an investigator as potentially related to the study treatment, they will be entered into the safety database for expedited purposes. Conversely, if the investigator considers the event not related to the study treatment, then it will be considered a non-case.

### 9 STATISTICS

### 9.1 Statistical Methods

Unless otherwise specified, descriptive statistics will include the number of non-missing observations, mean, standard deviation (SD), median, minimum and maximum values for the continuous/quantitative data or absolute and relative frequency counts and percentages for categorical/qualitative data.

Data handling and evaluation procedures will be described in the Statistical Analysis Plan (SAP).

# 9.1.1 Demographic and Baseline Characteristics

Demographic and baseline characteristics will be summarized by treatment. For quantitative variables, mean, SD, median, and minimum/maximum will be provided. For qualitative variables, the frequency and percentage will be provided.

# 9.1.2 Efficacy Analysis

The primary efficacy analyses will be performed using the Modified Intent-to-Treat (mITT) population (see Section 9.5 for the definition of the mITT population). Additionally, the primary efficacy endpoint will be also analyzed using the Per-Protocol (PP) population (if different from the mITT population, see Section 9.5 for the definition of the PP population). For sensitivity analysis, the primary efficacy endpoint will be analyzed using the Intent-to-Treat (ITT) population (see Section 9.5 for the definition of the ITT population). For subjects

in both treatment groups in the ITT population who do not meet the intra-operative criteria and do not receive the study treatment, they will be deemed as not achieving hemostasis for the primary efficacy endpoint.

The primary efficacy endpoint of hemostasis at TBS by T4 will be analyzed using the Cochran-Mantel-Haenszel (CMH) test stratified by type of surgery (i.e., parenchymous versus soft tissue surgery). The ratio of the proportion of subjects meeting the primary efficacy endpoint in the 2 treatment groups (FS Grifols relative to EVICEL) and its 2-sided asymptotic 95% CI will be provided. The non-inferiority will be deemed to have been demonstrated if the lower limit of the 95% CI exceeds 0.8. After the non-inferiority of FS Grifols to EVICEL is established, its superiority may be additionally claimed if the 95% CI for the ratio is entirely above 1.

Secondary efficacy endpoints will be analyzed by similar methods at other individual assessment time points (i.e.,  $T_7$  and  $T_{10}$ ).

Exploratory efficacy endpoints will be descriptively summarized by treatment group. The proportion of subjects achieving at least 1 point decrease in bleeding intensity according to the 5-point validated bleeding severity scale by each of the defined observation time points (i.e., T4, T7 and T10) will be analyzed using CMH test stratified by type of surgery (i.e., hepatic versus soft tissue surgery).

Also, an ordered categorical analysis of the hemostatic status at each of the assessment time points (i.e.,  $T_4$ ,  $T_7$  and  $T_{10}$ ) will be presented. For this, the subjects will be assigned to 1 of 4 categories on the basis of their TTH (0 to  $\leq$ 4 minutes;  $\geq$ 4 to  $\leq$ 7 minutes;  $\geq$ 7 to  $\leq$ 10 minutes;  $\geq$ 10 minutes).

Prevalence of treatment failures will be summarized and analyzed by treatment group.

### 9.1.3 Safety Analysis

The safety analyses will be based on the Safety population (see Section 9.5 for the definition of the Safety population). The safety analyses will be addressed by listing and tabulation of AEs and includes suspected ADRs, vital signs, physical assessments, and clinical laboratory tests. Data will be described using descriptive analyses.

### 9.1.3.1 Adverse Events

Adverse events will be coded and classified using MedDRA terms (system organ class and preferred terms).

When a causal relationship of an AE is classified by the investigator as definitively or possibly related, the event will be defined as a suspected ADR. A suspected ADR with a causal relationship of "definitively" will be defined as an AR. The sponsor will consider the investigator's causality assessment and also provide its own assessment. If there is any disagreement in causality assessment between the investigator and the sponsor, separate summary of suspected ADRs/ARs will be provided.

For summary purpose, AEs will be classified as TEAEs or non-treatment-emergent AEs (non-TEAEs) depending on the comparison of AE onset date/time with the start date/time of study treatment with the IP. A TEAE will be defined as an AE which occurs between the start of study treatment and the final visit of the clinical trial. A non-TEAE will be defined as an AE which occurs prior to the start of study treatment. Non-TEAEs and TEAEs will be summarized separately.

The incidence of TEAEs and suspected ADRs/ARs will be summarized by each treatment group, system organ class, preferred term, causal-relationship, intensity (severity) and seriousness (serious vs non-serious) using descriptive statistics. At each level of summarization, a subject will only be counted once per system organ class or preferred term using the most severe AE or the AE with the strongest causal relationship to study treatment.

Subjects with a SAE, AEs leading to death, or who withdraw from the study because of an AE will also be individually listed and summarized.

All AEs will be individually listed.

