#### 9.1.3.4 Physical Assessment

Physical findings (normal and abnormal) will be listed for each clinical trial subject. Any clinically significant abnormality, as determined by the investigator, developed by an individual during the clinical trial and not already present at baseline will be reported as an AE.

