10.1 Adverse Events

All reported AEs will be coded and summarized by system organ class (SOC) and preferred term (PT) according to MedDRA.

When an AE is classified, assessing causal relationship by the investigator, as definitively or possibly related, the event will be defined as a suspected ADR. A suspected ADR with a causal relationship of "definitively" will be defined as an AR. When the causal relationship is labeled "Unrelated", then it will be considered that the AE is not imputable to the investigational medicinal product and it is not a suspected ADR. The sponsor will consider the investigator's causality assessment and also provide its own assessment. If there is any disagreement in causality assessment between the investigator and the sponsor, separate summary of suspected ADRs/ARs will be provided.

For summary purposes, AEs will be classified as treatment emergent AEs (TEAEs) or non-treatment emergent AEs (non-TEAEs) depending on the comparison of AE onset date/time with the start date/time of study treatment. A TEAE will be defined as an AE which occurred between the start of study treatment and the final visit of the clinical trial. Non-TEAEs and TEAEs will be summarized separately.

The incidence of TEAEs, suspected ADRs, ARs, and SAEs will be summarized by treatment group, SOC, and PT. Also, the incidence of TEAEs by causal-relationship, intensity (severity), and seriousness (serious vs non-serious) will be descriptively summarized. At each level of summarization, a subject will only be counted once per SOC or PT using the most severe AE, or the AE with the strongest causal relationship to study treatment.

Subjects with SAEs, AEs leading to death, and TEAEs leading to the discontinuation from the study will also be separately listed.

The TEAEs/suspected ADRs reported due to clinically relevant abnormal laboratory results, vital signs or physical assessments will be collected.

All AEs/suspected ADRs will be presented in a data listing.

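### Treatment emergence is decided by onset time alone, so an adverse event under way at TStart that worsens after application can drop out of the TEAE and investigator-rated suspected ADR tables

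*Protocol*

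**What the plan says.** Protocol 9.1.3.1 sorts AEs into two classes "depending on the comparison of AE onset date/time with the start date/time of study treatment with the IP". It then defines the classes: "A TEAE will be defined as an AE which occurs between the start of study treatment and the final visit of the clinical trial" and "A non-TEAE will be defined as an AE which occurs prior to the start of study treatment". SAP 10.1 makes the same onset comparison and says "A TEAE will be defined as an AE which occurred between the start of study treatment and the final visit of the clinical trial". Neither section mentions worsening.

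Protocol 8.3.8 sets the causality rule in a note to the list of AE fields in the eCRF: "Causality assessment will be made only when the AE occurs after the subject has received the study treatment". It continues: "An AE occurring before subject's exposure to study treatment will be always labeled as" unrelated.

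Under protocol 9.1.3.1 and SAP 10.1, an AE becomes a suspected ADR on the investigator's rating only if it is rated possibly or definitively related. For physical findings, protocol 9.1.3.4 covers a clinically significant abnormality "developed by an individual during the clinical trial and not already present at baseline will be reported as an AE".

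**The concern.** In many trials the first dose precedes most of the events of interest, and a rule based on onset does little harm. Here treatment starts in the middle of an operation. The child is already anesthetized, opened and bleeding at TStart, and AEs have been collected since consent (protocol 8.2.1). An AE can therefore be in progress when the sealant is applied.

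Protocol 2.3.2 names hypotension among the signs of hypersensitivity to a protein product such as this. A reaction could show as deepening of hypotension that was already present. If that stays one event with its first onset time, the part that matters for product safety is assigned to the period before the product was given, and its causality rating is fixed by rule rather than judged. Evaluating safety is a stated objective (protocol 3.2), and the main safety tables are the incidence of TEAEs and suspected ADRs.

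**Working it through.** The point turns on definitions. The plan has no figure to reproduce and no arithmetic applies. The check is to trace one case through the written rules.

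**Can the case arise?** Protocol 7.2.1.3.1 records vital signs and AEs just before skin incision. Section 7.2.1.3.2 records vital signs again when the bleeding site is identified. Section 7.2.1.3.3 records them 5 minutes after TStart. Under 8.2.3, a vital-sign abnormality judged clinically relevant is an AE. So an abnormality can be recorded as an AE before TStart and be seen to worsen after it.

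**Is there a rule for worsening?** I looked in protocol 8.2.1 to 8.2.4, 8.3.3, 8.3.4, 8.3.7, 8.3.8 and 9.1.3.1 to 9.1.3.4, and in SAP 3.2, 4.1 and 10.1. None makes a worsened event treatment-emergent, and none requires a new entry. Protocol 8.3.8 prefers that clearly related signs and symptoms be grouped as one diagnosis, which leans towards a single entry.

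**Test case.** A mild AE starts after incision and before TStart, and becomes severe after application. The documents allow two ways to record it:

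| | One entry, original onset | New entry at worsening |
|---|---|---|
| Class (protocol 9.1.3.1, SAP 10.1) | non-TEAE | TEAE |
| Investigator causality (protocol 8.3.8) | unrelated by rule | assessed |
| Can be a suspected ADR on the investigator's rating | no | yes |
| In TEAE incidence tables | no | yes |
| In SAP 10.1 listing of TEAEs leading to discontinuation, if the child is withdrawn for it | no | yes |
| In the listing of all AEs | yes | yes |
| In SAE listings, if serious | yes | yes |

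The same clinical course gives two classifications, and nothing in the documents decides between them. Sites may differ.

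**Physical findings.** Protocol 9.1.3.4 leaves out a finding that was present at baseline and has become worse. Protocol 8.2.4 makes any clinically relevant abnormal finding an AE without that limit, so the two sections do not match. This is secondary: Appendix 1 schedules physical examinations at baseline, Day 4 and Day 30, not during surgery.

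**The case against.** The strongest reply is that little is lost, and much of it stands.

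- Non-TEAEs have their own summary and all AEs are listed. SAEs and AEs leading to death are listed without restriction to TEAEs. Protocol 9.1.3.1 also lists withdrawals due to any AE; only the SAP listing is limited to TEAEs.
- Clinically relevant vital-sign and laboratory abnormalities are AEs under protocol 8.2.2 and 8.2.3, with no condition that they were absent before. A site may enter a worsening as a new AE. True, but no text requires it.
- Protocol 5.2 excludes children with major intra-operative complications that need resuscitation or a change to the planned procedure. That removes the gravest events before application and leaves the milder ones, which have room to worsen.
- Anaphylaxis, thromboembolism or disseminated intravascular coagulation arising after application would normally be a new diagnosis with its own onset, and so a TEAE.
- Scheduled laboratory samples are taken before incision and at Day 4, so they would not date an abnormality to the interval between incision and TStart. Vital signs are the better example.
- Change-from-baseline and shift summaries of vital signs and laboratory data do not depend on AE class.

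A reader might go further and infer that a serious reaction could bypass expedited assessment. The documents do not support that. Protocol 8.3.9.1 sends every SAE to the sponsor within 24 hours whatever its attribution, and 8.3.7 has the sponsor evaluate for expedited reporting any event that either party considers serious.

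A reader might also infer that such an event can never be a suspected ADR. That too is unsupported. Under protocol 8.3.4 and 9.1.3.1 and SAP 10.1 the sponsor makes its own causality assessment, and a disagreement leads to a separate summary. The note in 8.3.8 concerns the causality field in the eCRF, and no text says whether it binds the sponsor.

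**Conclusion.** The definition has a real gap. Followed as written, it puts an AE that is under way at TStart and worsens after application among the non-TEAEs whenever the site keeps one entry. The event then leaves the TEAE and investigator-rated suspected ADR incidence tables and the SAP listing of TEAEs leading to discontinuation.

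The consequence is possible under-counting in both arms. Its size cannot be estimated: the documents give no rate of AEs in progress at TStart and none for their later worsening. It would be zero if every site made a new entry each time. A count of affected children, or a comparison with the number of cases that would make a safety signal, would rest on assumed rates and on a threshold the documents do not define.

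The rule is the same in both arms and the safety analysis is descriptive (protocol 9.1.3), so the non-inferiority conclusion is not touched, and nothing here shows a tilt towards either product. Confidence is high that the clause is missing and low about how much it matters in practice. It is worth correcting because the change is small and the affected tables carry the main safety message.

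**What to change.** - **Protocol 9.1.3.1 and SAP 10.1:** define a TEAE as an AE that starts, or that worsens in severity or becomes serious, at or after TStart and up to the final visit. Define a non-TEAE as one that starts before TStart and does neither afterwards.
- **Protocol 8.3.8:** require such a worsening to be recorded as a new AE entry with its own onset date and time, severity, seriousness and causality. Limit the automatic unrelated rating to the pre-exposure entry.
- **Protocol 9.1.3.4:** align with 8.2.4, so that worsening of a physical finding present at baseline is also reportable.
- **eCRF completion guidance:** repeat the new-entry rule so that sites handle these events alike.

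The cost is a sentence or two in each document plus the guidance text. TEAE counts will rise slightly in both arms. No treatment procedure or efficacy analysis changes.
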